## DIFFERENCES BETWEEN DPP-IV INHIBITORS

Potency and Efficacy to inhibit DPP-IV enzyme

It is important to mention that all DPP-IV inhibitors are reversible competitive inhibitors and it is difficult to compare their effects when analyzing individual studies since the experimental conditions may be different; however, there is a study in which inhibitors were compared under identical conditions showing similar efficacy (maximum effect) to inhibit DPP-IV in vitro, although there were differences in potency, the most potent being linagliptin [88] .

#### Half life

As for the half-life, vildagliptin and saxagliptin [89] have shorter half-lives, however, linagliptin [90] and sitagliptin [91] have a longer duration of effect, which gives the latter two the ability to inhibit the DPP-IV enzyme for 24 hours at > 80%; although it is worth mentioning that in the original study that evaluated the half-life and potency of sitagliptin to inhibit DPP-IV was performed in healthy volunteers [91], unlike the original study in which the half-life and potency of linagliptin was evaluated for inhibit DPP-IV that was performed in patients with type 2 diabetes mellitus (DM2) [90], a scenario in which medications are usually used. However, it is important to mention that the activity in these assays is evaluated ex vivo and is generally not corrected by the dilution of the sample, so the actual inhibition of DPP-IV is expected to be even greater 15oc the measurement.

#### Selectivity and elimination route

The selectivity of the different DPP-IV inhibitors by this enzyme has been evaluated in in vitro studies and it has been reported that both linagliptin [88] and sitagliptin [92] are the ones that have the highest selectivity for the DPP-IV enzyme; linagliptin has a selectivity > 10,000 for DPP-IV 15oc for DPP-8/9 compared to sitagliptin which is >5550; This is important because the inhibition of these two DPP-8/9 enzymes is what theoretically has been thought to be associated with lymphocyte activity inhibition side effects, although this effect has not been observed in the clinic, since these 2 Enzymes are found at the 15oce15celular level [93-95]. On the other hand, linagliptin only has lower selectivity on the fibroblast activation protein  $\alpha$  (FAP $\alpha$ ) which is a protein that is not found in adult tissue so the implications of this data are even lower, since the inhibitors of DPP-IV are only indicated in adults. Sitagliptin, vildagliptin and saxagliptin are

eliminated in more 16oc 80% by the renal route, however, linagliptin is eliminated in more 16oc 80% by bile route, so it can be used in patients with any degree of renal insufficiency without 16oce adjustment and without losing the pharmacological effect. [96].

## CLINICAL ASPECTS OF DPP-IV INHIBITORS

### Clinical efficacy

Regarding the clinical efficacy and the ability of different DPP-IV inhibitors to reduce HbA1c, fasting glucose and postprandial glucose, various meta-analyzes and clinical studies have shown similar efficacy, achieving a reduction in HbA1c of between 0.5 - 1.0% ( $\approx 0.8\%$ ), with greater reductions when baseline values are higher [93-95, 97, 98].

### Side effects and safety

So far, no greater cup of side effects have been found with DPP-IV inhibitors compared to control groups, and likewise, no differences in side effects have been reported between the various DPP-IV inhibitors [93, 94, 97, 98]; In addition, its safety regarding the risk of pancreatitis and pancreatic cancer has been validated by the FDA and the European Medicines Agency recently [99].

TABLE 1. Differential characteristics between DPP-IV inhibitors

NAME	POWE R (IC50)	DO SE	EFFECTIVE NESS TO INHIBIT THE DPP-IV x 24h	MID DLE LIFE (h)	ELIMINA TION	SELECTI VITY	USE IN RENAL FAILURE	CLINICA L EFFECTI VENESS ON HB A1C
Linaglipt ina [90]	1Nm	5mg /24h	> 80 %	10 – 40	Bile > 80 %	Alta	Recomm ended	0.5 – 1.0 %
Sitaglipti na [91]	19nM	100 mg/ 24h	> 80 %	8 – 24	Renal > 80 %	Alta	Not recomme nded or adjust dose	0.5 – 1.0 %
Vildaglip	62nM	50m	> 80 %	1.5 –	Renal >	Media	Not	0.5 – 1.0

tina [89]		g/12 h		4.5	80 %		recommen ded	%
Saxagli ptina	50nM	5mg /24h	> 70 %	2 – 4	Renal > 80 %	Media	Not recommen ded or adjust dose	0.5 – 1.0 %

• **LINAGLIPTINE**

The mechanism of action of linagliptin is to inhibit the DPP-IV enzyme (dipeptidyl peptidase type IV); This enzyme (DPP-IV) has the biological effect of inactivating the glucagon-like peptide type 1 (GLP-1), so being inhibited by linagliptin this favors that the levels of endogenous GLP-1 rise up to 3.2 times by above the previous values (same that are reduced in patients with type 2 diabetes mellitus, which partly explains that these patients have a reduction in the incretin effect), which determines the biological effects of GLP-1 as stimulation of insulin secretion by pancreatic beta cells and inhibition of glucagon secretion by pancreatic alpha cells. This effect on the stimulation in insulin secretion is totally dependent on glucose levels, so it does not cause hypoglycemia. Linagliptin has a half-life of 12 h so it can be used every 12 or 24 h, it is eliminated by bile in more than 70% so it can be used in patients with kidney disease without dose adjustment, it offers a potential for achieve a sustained inhibition of more than 90% in DPP-IV for 24 h and is highly selective to inhibit DPP-IV compared to other enzymes such as DPP-8 and DPP-9, their doses range from 2.5 to 5mg / day . Linagliptin is indicated in the treatment of patients with uncontrolled type 2 diabetes mellitus, which does not cover control goals such as: glycosylated Hb less than 7%, fasting glucose less than 110mg / dl and postprandial glucose less than 140mg / dl. It can be used as a combination therapy with metformin, sulfonylureas, thiazolidinediones and insulins, either as double or triple therapies.

A randomized clinical trial was conducted in the Mexican population comparing the effect of linagliptin with metformin in subjects with glucose intolerance. Sixteen subjects with glucose intolerance, overweight or obesity were included. They were randomized into 2 groups, one group was treated with metformin and another with linagliptin, both for 3 months. The group that was treated with linagliptin obtained a significant decrease in glucose at 120 min. [110]

## **OTHER THERAPIES WITH POTENTIAL CARDIOPROTECTOR IN PREDIABETES**

- **SGLT2 inhibitors (glucosuric)**

In addition to metformin, incretins and pioglitazone, it has been proposed that other recent therapies may also be useful in the treatment of the disease in early stages. These types of drugs include glucosurics, or inhibitors of the renal glucose transporter SGLT2. Under normal conditions, thanks to SGLT2 (97%) and SGLT1 (3%), all glucose that is filtered by the renal glomerulus is reabsorbed into the renal proximal tubules, so there should be no glycosuria; The glomerulus is capable, in a healthy person, of filtering about 140-160 g of glucose per day. There is a clinical disorder known as familial renal glycosuria, in which there is a mutation of SGLT2 that conditions glycosuria of up to 60-120 g per day, without these patients having any negative metabolic, hemodynamic or renal consequences. As part of the therapeutic innovations, SGLT2 inhibitors, or glucosurics, were developed, which are drugs that inhibit the activity of SGLT2 by 30-50%, thus reducing renal reabsorption of glucose and thereby favoring glycosuria. These types of medicines have been used for several years in the world and have revolutionized the treatment of DM2, which is what they are indicated for, by basing its effect on renal glucose elimination and not on the dependence of sensitivity to Insulin or insulin secretion. It has been shown that the patient with DM2 has a greater renal reabsorption of glucose in part due to the high regulation of SGLT2 by hyperglycemia [100]. There are few previous studies evaluating the usefulness of glucosurics in prediabetes; there is a report in patients with obesity, and mostly with prediabetes, who were treated with Dapagliflozin and an improvement in body weight, blood pressure and hyperglycemia frequency was observed [101, 102]; recently, another work was published with Empagliflozin, in patients with impaired fasting glucose in which the treatment for a few weeks substantially improved the function of pancreatic beta cells and therefore glucose metabolism [103]. Of this type of medication, Empagliflozin is particularly interesting, a drug that entered Mexico since 2015.

Empagliflozin has become an interesting drug because it is the only antihyperglycemic drug so far that has proven useful in reducing cardiovascular morbidity and mortality in

patients with DM2. and high cardiovascular risk [100, 104-107], and its main pharmacological characteristics are described below [100]:

- Mechanism of action: Empagliflozin inhibits approximately 30-50% of the activity of SGLT2, reducing renal reabsorption of glucose and favoring significant decreases in plasma glucose and glycosylated hemoglobin. Indirectly, it can improve insulin resistance and insulin secretion.

- **Dose:** 10, 12.5 or 25 mg every 24 hours; It can be consumed at any time of the day, with or without food.

- **Current indications:** Type 2 diabetes to improve metabolic control in patients with DM2 and a history of cardiovascular events. Its indication in patients with heart failure without DM2 is under evaluation.

- **Other beneficial effects:** Empagliflozin has been shown to significantly reduce cardiovascular morbidity and mortality and may also function as a nephroprotective, making it the only drug indicated in patients with DM2 and previous cardiovascular events to reduce the risk of a new cardiovascular event

- **Contraindications:** Patients with Type 1 Diabetes, patients hospitalized for severe glucose decompensation (diabetic ketoacidosis); There is no consensus on its use in children under 18 years of age, pregnant and breastfeeding, so it is not recommended. It is not indicated if there is significant renal involvement (creatinine clearance less than 30ml / min).

- **Side effects:** There is no risk of hypoglycemia, it can occur only when associated with insulin or sulfonylureas. A slightly higher frequency of genital infections has been observed in women, so if it is present, it is suggested to discontinue the medication.

A study conducted by Abdul-Goni et al. (2017) in which they used empagliflozin to reduce fasting plasma glucose and improve the function of beta cells in subjects with impaired fasting glucose. Sixteen subjects were studied, of which 8 had normal glucose levels and 8 had impaired fasting glucose. They were randomized into 2 groups, both received empagliflozin 25mg / d for 2 weeks, subjects with impaired fasting glucose had a significant decrease in fasting glucose and an improvement in the function of beta cells measured by the insulin availability index . [111].

A study conducted by DeFronzo et al. (2015), studied the safety and efficacy of the empagliflozin / linagliptin combination as therapy in subjects with DM2 not controlled with metformin. They were randomized to a combination of empagliflozin 25 mg / linagliptin 5 mg (n = 137), empagliflozin 10 mg / linagliptin 5 mg (n = 136), empagliflozin 25 mg (n = 141), empagliflozin 10 mg (n = 140), or linagliptin 5 mg (n = 132) as a complement to metformin (> 1,500 mg / day) for 52 weeks. The primary end point was the change from the start in HbA1c at week 24. At week 24 the reductions in HbA1c were significantly greater for empagliflozin 25 mg / linagliptin 5 mg (-1.19%). The efficacy remained until week 52. The proportion of subjects with adverse events (gastroenteritis, hypertension, headache, diarrhea and constipation) during the 52 weeks was similar in all groups, without hypoglycemia as adverse events [112].

The study conducted by Kaku K. et al. (2019) evaluated the efficacy and safety of empagliflozin and linagliptin fixed dose combinations in Japanese patients with poorly controlled type 2 diabetes mellitus (HbA1c  $\geq 7.5 \leq 10.5\%$ ). They were randomized into 4 treatment groups: 1) empagliflozin 10mg / placebo, 2) empagliflozin 25mg / placebo, 3) empagliflozin 10mg / linagliptin 5mg and 4) empagliflozin 25mg / linagliptin 5mg. The change from baseline HbA1c at week 24 was greater (P <.0001) with Empagliflozin / Linagliptin than with Empagliflozin / Placebo (Empagliflozin 10mg / Linagliptin 5mg: -0.94% vs. -0.12%; adjusted mean difference, - 0.82%; Empagliflozin 25mg / Linagliptin 5mg: -0.91% vs. -0.33%; adjusted mean difference, -0.59%). During periods of 24 and 52 weeks, higher proportions of patients reached HbA1c <7.0% and greater decreases in fasting blood glucose were observed with Empagliflozin / Linagliptin compared to Empagliflozin / Placebo. These results support the combination of a fixed dose Empagliflozin / Linagliptin as a potential option for Japanese patients with DM2 who require combination therapy. [113]

Lingvay I. (2017) conducted a non-systematic review of the literature focusing on a fixed-dose combination of SGLT2 inhibitors and DPP-4 inhibitors available in the United States. SGLT2 inhibitors and DPP-4 inhibitors have complementary mechanisms of action that address several of the underlying pathophysiological abnormalities present in DM2 without overlapping toxicities. Trials of cardiovascular outcomes reported to date

support the safety of the DPP-4 class and suggest possible cardioprotective effects for SGLT2 inhibitors, at least based on the first reported study, which used empagliflozin. Recently, clinical evidence shows that SGLT2 inhibitor / DPP-4 inhibitor therapy is an effective combination for treatment with DM2, which provides reductions in glycosylated hemoglobin (HbA1c) from 1.1% to 1.5% and weight reductions of approximately 2 kg when added to metformin. [114]

### **RESEARCH QUESTION**

What is the effect of quadruple therapy (linagliptin + empagliflozin + metformin + lifestyle modifications) compared to standard therapy (metformin + lifestyle modifications) on pancreatic islet function, insulin resistance and cardiovascular function in patients with mixed prediabetes and obesity?

### **JUSTIFICATION**

DM2 is a chronic disease that has reached global epidemic proportions due to the growing number of patients in all countries; It has become the disease that causes more chronic and acute complications to patients, consuming a large percentage of health spending in countries such as Mexico, generates a large number of disabilities at productive ages and is one of the main causes of cardiovascular morbidity and mortality.

The best strategies will be those that are aimed at early stages of the disease, because it will involve raising awareness in the population and having more impact on the stability and / or reversibility of pathophysiological alterations, which will ultimately result in a lower incidence of DM2.

Some studies have been carried out on prevention of DM2 based on lifestyle modifications, some of them have used strategies with a very narrow and intensive follow-up, which limits the durability of adherence to the intervention and hinders the practical applicability of the measures , have not compared the effect of some of the medications that have so far shown more efficacy for this purpose and in some of these

studies the doses used are frequently associated with the occurrence of side effects; of these studies, none have been carried out in Mexico, so if the combination of drugs with additive pathophysiological impact plus cardiovascular protection is used in early stages, better results can be obtained and with greater impact on the natural history of the disease with a view to a long-term follow-up that yields measures that may have an applicability in clinical practice, with the purpose of contributing to the control of this global epidemic that is surpassing health systems, especially in developing countries such as Mexico.

The combination of medications with different mechanisms of action, in low doses with lifestyle modifications could be a useful strategy not only to prevent DM2, but also to prevent macro and microvascular complications early.

## **OBJECTIVES**

### **Goal:**

To assess the effect of quadruple therapy (linagliptin + empagliflozin + metformin + lifestyle modifications) compared to standard therapy (metformin + lifestyle modifications) on pancreatic islet function, insulin resistance and cardiovascular function in patients with mixed prediabetes and obesity.

### **Specific goals:**

1. Identify patients with glucose intolerance and obesity who may enter the study.
2. To assess the effect at 12 months with treatment with metformin 1700 mg / d and lifestyle modifications on insulin resistance, pancreatic islet function, and cardiovascular function in a group of patients with mixed prediabetes and obesity.
3. To assess the effect at 12 months of treatment with the combination of linagliptin 2.5 mg / metformin 850 mg every 24 h + Empagliflozin 12.5 mg / metformin 850 mg every 24 h and lifestyle changes on insulin resistance, the function of Pancreatic islet and cardiovascular function in a group of patients with mixed prediabetes and obesity.

4. Evaluate and compare cardiovascular risk markers (TNF $\alpha$ , IL6, hsPCR) before and after treatments in the 2 study groups.
5. Compare insulin resistance and pancreatic islet function between the study groups at the end of the intervention.
6. Evaluate and compare glucose metabolism using OGTT at the beginning and end of treatment in the study groups.

### **Secondary objectives**

- Evaluate the percentage of patients who recovered glucose normotolerance after the intervention in each of the study groups.
- Evaluate and compare the changes in body composition, through body composition analysis by DEXA, in the two study groups at the beginning and at the end of the intervention.
- Evaluate therapeutic adherence in the study groups.

### **HYPOTHESIS**

Quadruple therapy (linagliptin + empagliflozin + metformin + lifestyle modifications) has a greater effect on pancreatic islet function, insulin resistance and cardiovascular function compared to standard therapy (metformin + lifestyle modifications) in patients with mixed prediabetes and obesity.

### **MATERIAL AND METHODS**

**Type of study:** Single Center Parallel Clinical trial, randomized, double blind

**Study universe:** Mexican patients with mixed prediabetes and obesity.

**Study population:** Mexican patients with mixed prediabetes and obesity, from the State of Guanajuato.

**Location:** Regional High Specialty Hospital of Bajío and Division of Health Sciences of the University of Guanajuato, León, Gto.

**Type of sampling:** Non-probabilistic, of consecutive cases.

**Sample size:** The sample size calculation was performed based on the formula to compare proportions. We expect that quadruple therapy (linagliptin + empagliflozin + metformin + lifestyle modifications), improve at least 75% the outcome variables (insulin resistance, pancreatic islet function and cardiovascular function), at 6 months of initiated the intervention, as long as the standard therapy (metformin + lifestyle modifications) achieves only 30% [69-71, 73], so that the study is designed to detect a minimum difference of 45% between the study groups with a type I (alpha) error of 0.05 and a sample power of 80%, and according to the following formula [108]:

$$n = \frac{(Z_{\alpha/2} + Z_{\beta})^2 p_1(1-p_1)(r + 1)}{(d)^2 r}$$

Where,

$$(Z_{\alpha / 2} + Z_{\beta})^2 = 7.9$$

p1 = proportion of individuals in the best treatment who did not achieve improvement = 0.25

p2 = proportion of individuals in the worst treatment who did not achieve improvement = 0.70

r = ratio of individuals in the treatment groups = 1

d = difference expected to be found = 0.45

n = 14 + 20% of losses = 17 patients per group

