#### 5) Insulin Sensitivity (Matsuda Index)

- a. Type of variable and level of measurement: Dependent, Quantitative of reason
- b. Indicator: natural numbers
- c. Conceptual definition: The ability of insulin to promote glucose uptake by muscle tissue, to suppress glucose production by the liver and to prevent lipolysis in adipose tissue.
- d. Operational definition: It will be evaluated using the Matsuda index with glucose and insulin values during the OGTT using the following formula:

$$\text{Insulin sensitivity} = \frac{10000}{\sqrt{(G_0 \times I_0) \times (G_{0-120} \times I_{0-120})}}$$

Where  $G_0$  = basal glucose

$I_0$  = basal insulin

$G_{0-120}$  = average glucose during OGTT

$I_{0-120}$  = average insulin during OGTT

This measurement will be carried out at the beginning and at the end of the intervention in each of the study groups.

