## **7) Cardiovascular function**

- a. Type of variable and level of measurement: continuous quantitative
- b. Indicator: %
- c. Conceptual definition: Comprehensive evaluation of the mechanical function of cardiac function, whose objective is to predict the risk of future cardiovascular events.
- d. Operational definition: It will be evaluated by the left ventricular ejection fraction, ventricular mass and diastolic and systolic preloads, by standard echocardiography performed by HRAEB Echocardiographic Cardiologist

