## **STATISTIC ANALYSIS**

The data will be presented with descriptive statistics, mean and standard or median deviation and interquartile range, as well as percentages and incidence. For comparisons of numerical variables between the study groups, we will use Student's t if the distribution of the data follows a normal pattern, otherwise the Mann-whitney U test will be used; To compare qualitative variables we will use Chi square. Delta analysis will be performed for differences between groups. It will be considered significant when the value of p is  $<0.05$ . For the analysis and presentation of the data we will use the SPSS Version 15 and GraphPad Prism 5 programs.

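### The stated 80% power is for a proportion improved, but the three outcomes it names are quantitative, have no responder cut-off and will be compared by t or Mann-Whitney tests, so their power is undefined

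*Combined protocol and SAP*

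**What the plan says.** **Sample size (Material and Methods).** The trial is sized by a two-proportion formula: "The sample size calculation was performed based on the formula to compare proportions". The quantity compared is improvement in "the outcome variables (insulin resistance, pancreatic islet function and cardiovascular function), at 6 months of initiated the intervention". The paragraph sets "a type I (alpha) error of 0.05 and a sample power of 80" per cent, and its inputs are failure rates: "p1 = proportion of individuals in the best treatment who did not achieve improvement = 0.25", against 0.70 in the comparator. The result is 14 per group, or 17 after adding 20% for losses. These three domains are also the ones named in the Hypothesis.

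**Dependent Variables.** Both beta-cell indices and the Matsuda index carry the entry "Type of variable and level of measurement: Dependent, Quantitative of reason". Cardiovascular function carries "Type of variable and level of measurement: continuous quantitative". The single dichotomous variable is the first on the list, improvement in glucose metabolism. It is Yes only if fasting glucose is below 100 mg/dl and 2-hour glucose below 140 mg/dl at 12 months.

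**Statistic Analysis.** Numerical variables are compared between groups by Student's t "if the distribution of the data follows a normal pattern, otherwise the Mann-whitney U test will be used". Qualitative variables go to chi-square. A delta analysis is mentioned for between-group differences.

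**The concern.** A power figure belongs to one test of one endpoint at one time. Here the endpoint is the proportion of patients improved in three domains at 6 months. Nothing in the plan turns an insulin index or an echocardiographic measure into improved or not improved, and the Statistic Analysis section sends those variables to tests of location. The test that was powered is not the test that will be run on those outcomes.

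This is the only power statement in the plan, and it concerns the trial's main hypothesis. An ethics committee or reader will take it to mean that the comparisons of insulin resistance, islet function and cardiovascular function each have 80% power. The plan gives no SD and no expected mean difference for any of them, so nobody can tell what differences the trial can detect. A non-significant result would then be hard to interpret.

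**Working it through.** **1. Reproduce the plan's figure.** All inputs are from the Sample size paragraph: (Zα/2 + Zβ)² = 7.9, p1 = 0.25, r = 1, d = 0.45.

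n = 7.9 × 0.25 × 0.75 × 2 / 0.45² = 2.9625 / 0.2025 = 14.63

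The plan gives 14. Then 14 × 1.20 = 16.8, given as 17. The figures reproduce, apart from rounding down.

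**2. Match the powered comparison to the planned tests.**

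| | Sample size paragraph | Three named domains as defined | Only Yes/No dependent variable |
|---|---|---|---|
| Endpoint | improved in the three domains | beta-cell indices, Matsuda index, echocardiographic measures | regression of fasting hyperglycemia and glucose intolerance |
| Scale | proportion | quantitative | proportion |
| Cut-off for improved | none given | none given | given |
| Time | 6 months | end of the 12-month intervention (also measured at 6 months) | 12 months |
| Test | two proportions | Student's t or Mann-Whitney | chi-square |
| Stated rates | 75% and 30% | none | none |

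No planned test shares endpoint, scale and rates with the comparison that was powered. The rates are referenced to four diabetes-prevention trials. The protocol's own Treatment of Prediabetes section describes these by reduction in diabetes risk, so they supply no responder definition for the three domains either.

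**3. What the planned t-test can detect.** For a true difference of δ SD and n per arm, two-sided 5%, power follows the noncentral t distribution with 2n − 2 degrees of freedom and noncentrality δ√(n/2). The documents give no SD, so δ is shown over an assumed range.

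| True difference (SD) | Power, 14 per arm | Power, 17 per arm |
|---|---|---|
| 0.5 | 25% | 29% |
| 0.8 | 53% | 62% |
| 1.0 | 72% | 81% |
| 1.2 | 86% | 92% |

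The difference detectable at 80% power is 1.10 SD with 14 per arm and 0.99 SD with 17.

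**4. Translate the plan's rates to the SD scale.** Suppose improved means passing one common threshold on a normal variable with equal SD in both arms. Then 75% versus 30% implies a shift of z(0.75) − z(0.30) = 0.674 + 0.524 = 1.20 SD. The t-test power at that shift is 86% with 14 per arm and 92% with 17. The documents do not make this assumption. It shows only that the mismatch need not mean low power.

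**The case against.** The strongest defence has three parts.

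*A two-proportion test is planned.* Chi-square is in the Statistic Analysis section, a Yes/No variable heads the list of dependent variables, and recovery of normal glucose tolerance is a secondary objective. This stands, and it rules out saying that the plan contains no comparison of proportions. It does not rescue the 80%: that variable is not among the three domains, is read at 12 months, and has no rates of 75% and 30% stated for it.

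*Sizing on a dichotomy and testing the continuous variable is usually conservative.* On the assumption in step 4, the t-test does better than 80%. This also stands. A reader might infer from the mismatch that the main comparisons are underpowered. The documents do not support that, because they give neither an SD nor an expected mean difference.

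*The plan openly aims at a very large effect.* It says that it is designed for a 45-point difference. Power of 25% to 53% at 0.5 to 0.8 SD comes from having 14 to 17 patients per arm, not from the mismatch of scales, and the plan never claims 80% power for such differences. A reader might also want to express the limit in ejection-fraction points. The plan gives no SD for that measure, so no such figure can be supported.

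A separate weakness in the same paragraph is that the formula uses the variance of one arm for both. At the plan's own rates, a pooled two-proportion test has about 68% power at 14 per arm and 77% at 17. The present point does not depend on this.

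**Conclusion.** The power statement is wrong as written. It gives 80% for a comparison of proportions that is not planned on the outcomes it names, and the one planned comparison of proportions is on another endpoint at another time. Power for the planned tests of the hypothesis is therefore undefined. This follows from the text alone and needs no distributional assumption.

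Power is not proven too low. For the t-test, the trial reaches 80% at a true difference of 1.10 SD with 14 completers per arm, or 0.99 SD if all 17 finish. Those figures assume normality, equal variances, a two-sided 5% level and no adjustment for testing several outcomes. Whether differences of that size are plausible cannot be judged from the documents.

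**What to change.** In the Sample size paragraph, replace the 75% versus 30% power statement with text such as:

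> For the between-arm t-test of each quantitative outcome at 12 months, 14 completers per arm give 80% power (two-sided 5%, no multiplicity adjustment) for a difference of 1.10 SD of the variable analysed (the SD of change where deltas are compared), and 17 per arm for 0.99 SD. With 14 per arm, power is 53% at 0.8 SD and 25% at 0.5 SD. The Mann-Whitney test is slightly less powerful under normality.

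In the Statistic Analysis section, add that between-arm differences will be reported with 95% confidence intervals and that a non-significant result will not be read as absence of effect.

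Do not quote a baseline-adjusted detectable difference or one in ejection-fraction points unless that analysis and an SD are added to the plan. Defining a responder cut-off for each domain and testing it by chi-square would also remove the mismatch, but the cut-offs and a new calculation would then be needed.

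The cost is one reworded paragraph and one added sentence. Enrolment, visits and measurements stay as they are. The downside is that the stated sensitivity will look less favourable.
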